6.2.2 Dosage

To minimize the risk of immediate hypersensitivity reactions (including infusion reactions), the infusion used in this study will have a concentration of [REDACTED]

[REDACTED]. As a starting point, all dose levels will be given [REDACTED], while the duration of the infusion will be adapted accordingly. A decision can be taken by the Safety Advisory Committee during the study to reduce the infusion rate, as described in [Section 7.2.2.5.1](#). All study subjects will be closely observed for potential immediate hypersensitivity reactions, and all dosing will occur in a clinical site with experience in managing AEs.

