7.2.8 Vital signs

Vital signs (systolic and diastolic blood pressure, pulse rate, respiratory rate, and body temperature) will be evaluated at the following timepoints: screening, pre-dose, every 15 minutes during the infusion (e.g., 15, 30, 45, 60, 75, 90, 105, etc.), at the end of infusion and 30 min, 1, 2, 3, 4, 6, 8 and 20 hours after the end of the infusion and 5, 7, 14, 28, 56, and 84 days post-dose and in case of early termination visit.

Blood pressure will be measured in duplicate, after 5 minutes in the supine position. The single values and the average of duplicate blood pressure measurements will be reported in eCRF, and the average will be used to assess the subject's eligibility.

Clinical Study Code No.: CLI-10067AA1-01	Version No.: 6.0
EUDRACT No.: 2022-001079-15	Date: 06 July 2023

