3.3 VITAL SIGNS

3.3.1 *Available data*

The following vital signs parameters are collected:

- duplicate systolic (SBP) and diastolic blood pressure (DBP) in supine position.
- pulse rate.
- respiratory rate.
- body temperature.
- oxygen saturation.

Vital signs (blood pressure, pulse rate, respiratory rate, body temperature): systolic and diastolic blood pressure will be evaluated in duplicate after 5 minutes in supine position. Vital signs will be measured at the following timepoints: screening, pre-dose, every 15 minutes during the infusion (e.g., 15, 30, 45, 60, 75, 90, 105, etc.), at the end of the infusion and 30 min, 1, 2, 3, 4, 6, 8, and 20 hours after the end of the infusion and 5, 7, 14, 28, 56, and 84 days post-dose.

Oxygen saturation: will be measured at screening and continuous monitoring will occur from pre-dose to 10 hours post-dose at the following timepoints: pre-dose, every 15 minutes during the infusion (e.g., 15, 30, 45, 60, 75, 90, 105, etc.), at the end of the infusion and 30 min, 1, 2, 3, 4, 6, 8, hours after the end of infusion. Oxygen saturation will also be measured at 20 hours after the end of infusion, and 5, 7, 14, 28, 56 and 84 days post-dose and in case of early termination visit.

3.3.2 *Derivation rules*

Mean values of the duplicates will be calculated per time point and rounded as detailed in section 6.3.4. Records belonging to the same duplicate will be identified using variable VSREFID. All records of the duplicate will be used to calculate the mean, even if less or more than the expected two. The date and time of the first member of the duplicate will be assigned to this mean value. Throughout the analysis, including the derivation of baseline and abnormalities, the mean values will be used. Individual duplicate values will only be listed.

The following change from baseline abnormality categories will be defined:

- Changes from baseline:
 - Diastolic blood pressure
 - Decrease from baseline >10 mmHg
 - Increase from baseline >10 mmHg
 - Systolic blood pressure
 - Decrease from baseline >20 mmHg
 - Increase from baseline >20 mmHg

3.3.3 *Presentation of results*

Vital signs and oxygen saturation parameters will be summarised by means of descriptive statistics at each analysis time point by treatment. Actual values (with 2-sided 95% CI) and changes from baseline (with 2-sided 95% CI) will be tabulated.

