For the blood pressure parameters, the number and percentage of subjects with abnormal changes from baseline will be presented at each post-baseline time point and at the worst-case analysis visit by treatment.

All vital signs data will be listed.

Graphs of the mean changes from baseline over time will be prepared for the vital signs and oxygen saturation parameters by treatment. In addition, individual graphs of the changes from baseline over time will be presented by treatment for the vital signs and oxygen saturation parameters.

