Per parameter and analysis window, the value closest to the target time will be used in analysis tables and figures, other values will only be listed. If more than one value is located at the same distance from the target, then the latest in time will be selected. The value latest in time will be identified using, in order of preference, the assessment time, the visit and time point label or the group identifier. Missing values are removed before the selection is made.

Partially missing assessment dates or times disabling allocation to analysis windows will not be imputed and thus these assessments will not be considered in the per-time point analysis, except for the derivation of the worst.

6.2.5 *Worst-case*

A worst-case analysis visit (presented in the analysis as ‘At Any Time Point’, or similar) will be created for parameters for which abnormalities are defined to summarise values considered as the worst-case.

The worst-case analysis visit will be derived within the treatment phase, including scheduled and unscheduled assessments as well as the early termination visit assessments. Only post-baseline assessments will be considered for the worst-case analysis visit.

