6.4.2 Presentation of treatments

The following treatment labels will be used in the tables, listings and figures:

- CHF10067 1000 mg
- CHF10067 2000 mg
- CHF10067 3000 mg
- CHF10067 Total ⁺
- Placebo ^{*}
- Overall [#]

⁺ “CHF10067 Total” is the combination of “CHF10067 1000mg”, “CHF10067 2000mg” and “CHF10067 3000mg” treatment groups, will be shown for all demographics and safety tables (with the exception of disposition, analysis set, protocol deviations and PK).

^{*} All placebo subjects (from all cohorts) will be pooled into one “Placebo” group for presentation in tables and figures.

[#] Unless specified otherwise, an “Overall” column, to summarise all subjects over treatments (including placebo), will be presented only in tables showing data that are not affected by the study treatment (i.e., general characteristics analyses). The overall column will be shown last.

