14.3.3.1	Vital Signs and Oxygen Saturation: Summary of Actual Values and Changes from Baseline (Safety Set) Descriptive statistics of vital signs and oxygen saturation actual values and changes from baseline per parameter and analysis time-point. Table sorted by analysis time-point. Each parameter will begin on a new page.	SAF	VST001
14.3.3.2	Blood Pressure: Summary of Abnormal Changes from Baseline (Safety Set) [KFR] Tabulation of the blood pressure abnormalities as defined in section 3.3.2 at each post-baseline analysis time point and at the worst-case analysis time point per parameter. Table sorted by analysis time point. Each parameter will begin on a new page. Only post-baseline analysis time points are shown.	SAF	VST004
ECG			
14.3.4.1	12-Lead ECG: Summary of Actual Values and Changes from Baseline (Safety Set) [KFR] Descriptive statistics of continuous 12-lead ECG (HR, PR, QRS, QTcF) actual values and changes from baseline per parameter and analysis time point. Table sorted by analysis time point. Each parameter will begin on a new page.	SAF	EGT002
14.3.4.2	QTcF: Abnormalities (Safety Set) Tabulation of the abnormalities as defined in section 3.4.2 at each post-dose analysis time point and at the worst-case analysis time-point. Table sorted by analysis time point. Only baseline and post-dose analysis time points are shown.	SAF	EGT007
14.3.4.3	QTcF: Abnormal Changes from Baseline (Safety Set) [KFR] Tabulation of the QTcF change abnormalities as defined in section 3.4.2 at each post-baseline analysis time point and at the worst-case analysis time point. Table sorted by analysis time point. Only post-baseline analysis time points are shown.	SAF	EGT008
LUNG FUNCTION			
14.3.5.1	Spirometry: Summary of Actual Values and Changes from Baseline (Safety Set) Descriptive statistics of spirometry parameters actual values and changes from baseline per parameter and analysis time point. Table sorted by analysis time point. Each parameter will begin on a new page.	SAF	TPT001

	Statistical Analysis Plan		
CLI-10067AA1-01	Final Analysis	Final 1.0	of 30MAY2024

Number	Title	Analysis Set	TLFs Library Template Number
14.3.5.2	Spirometry: Summary of Relative Changes from Baseline (Safety Set) [KFR] Descriptive statistics of relative changes from baseline in spirometry results per parameter and analysis time point. Table sorted by analysis time point. Only post-baseline analysis time points are shown.	SAF	TPT004

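### If infusions lengthen with dose, the any-time row of the key blood-pressure table has a small upward gradient across doses in its expected counts, even with no drug effect

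*SAP*

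**What the plan says.** **Infusion length.** Protocol 6.2.2 describes a starting mode of administration for all dose levels (redacted), "while the duration of the infusion will be adapted accordingly". It adds: "A decision can be taken by the Safety Advisory Committee during the study to reduce the infusion rate". No duration per dose is visible.

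**Readings.** Protocol 7.2.8 has blood pressure taken "every 15 minutes during the infusion", with no upper limit. SAP 3.3.1 repeats this: "every 15 minutes during the infusion (e.g., 15, 30, 45, 60, 75, 90, 105, etc.), at the end of the infusion". From the end of infusion the schedule is the same for every cohort. The SAP 6.2.4 windows provide for up to 5.5 h of infusion, and the last window is open to the end of infusion.

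**The summary.** SAP 3.3.2 defines four categories: a systolic increase or decrease of more than 20 mmHg, and a diastolic increase or decrease of more than 10 mmHg. SAP 3.3.3 tabulates them: "abnormal changes from baseline will be presented at each post-baseline time point and at the worst-case analysis visit by treatment". SAP 6.2.5 states: "The worst-case analysis visit will be derived within the treatment phase, including scheduled and unscheduled assessments", together with early-termination assessments. Protocol 12.3.5.6 also asks for a count at any post-dose time point. The result is Table 14.3.3.2, "Blood Pressure: Summary of Abnormal Changes from Baseline (Safety Set) [KFR"], one of the outputs marked as a key first result.

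**Placebo.** SAP 6.4.2: "All placebo subjects (from all cohorts) will be pooled into one" column. Each cohort has 6 active and 2 placebo subjects.

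**The concern.** A count of subjects with at least one abnormal reading depends on how many readings each subject has. If infusion length rises with dose, so does the number of 15-minute readings, and the any-time row gives higher-dose subjects more opportunities to cross a fixed threshold by ordinary variation. Nothing in the SAP limits the row to a common schedule or shows how many readings lie behind each count.

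Safety and tolerability is the primary objective, and dose groups are read side by side without a formal test. A gradient produced by the measurement schedule points the same way as a dose-related blood-pressure effect. Pooled placebo mixes three schedules, and only 2 of its 6 subjects belong to the 3000 mg cohort.

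**Working it through.** The plan states no figure for this row, so there is none to reproduce. The check counts readings per subject and then finds the chance of at least one abnormal change when the drug does nothing.

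**Inputs from the documents**
- Readings common to all cohorts: end of infusion (1), then 30 min and 1, 2, 3, 4, 6, 8 and 20 h (8), then Days 5, 7, 14, 28, 56 and 84 (6). Total 1 + 8 + 6 = 15.
- Readings before end of infusion: one every 15 minutes.
- Thresholds: more than 20 mmHg systolic and more than 10 mmHg diastolic, with increases and decreases counted separately.

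**Assumptions not in the documents**
- Duration is proportional to dose, with the 3000 mg infusion lasting 5.5 h, 3 h or 1.5 h.
- Within-subject SD is 6, 8 or 10 mmHg systolic and 4, 5 or 6 mmHg diastolic.

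**Step 1: scheduled readings per subject.** With 5.5 h at 3000 mg, the durations are 110, 220 and 330 min. 110/15 gives 7 readings and 220/15 gives 14. 330/15 = 22, but the last coincides with end of infusion, leaving 21. The other cases follow in the same way.

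| Longest infusion | Before end of infusion (1000/2000/3000 mg) | Total, adding 15 |
|---|---|---|
| 5.5 h | 7 / 14 / 21 | 22 / 29 / 36 |
| 3 h | 3 / 7 / 11 | 18 / 22 / 26 |
| 1.5 h | 1 / 3 / 5 | 16 / 18 / 20 |

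**Step 2: independent readings, as a simple reference.** P(any) = 1 − (1 − p)^k. For k = 22, 29, 36 this gives 19.8%, 25.3%, 30.4% at p = 1%, and 48.8%, 58.7%, 66.6% at p = 3%. This overstates the gradient, because readings in one subject are correlated and all changes share one baseline.

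**Step 3: correlated readings.** Simulation of 40,000 subjects per dose, with change taken from a single pre-dose value. Within-subject variance is half independent noise and half exponentially correlated (time constant 2 h). Chance of at least one increase above threshold:

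| Parameter, SD, longest infusion | 1000 mg | 2000 mg | 3000 mg |
|---|---|---|---|
| Systolic, 6 mmHg, 5.5 h | 7.8% | 9.3% | 10.7% |
| Systolic, 8 mmHg, 5.5 h | 25.4% | 28.5% | 31.5% |
| Systolic, 10 mmHg, 5.5 h | 42.8% | 46.3% | 49.2% |
| Systolic, 8 mmHg, 3 h | 24.1% | 25.4% | 28.0% |
| Systolic, 8 mmHg, 1.5 h | 22.9% | 23.7% | 24.9% |
| Diastolic, 5 mmHg, 5.5 h | 42.8% | 46.5% | 49.1% |

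**Step 4: size in subjects.** Systolic, SD 8, 5.5 h: 6 × (0.315 − 0.254) = 0.37 subjects. The same at 1.5 h: 6 × (0.249 − 0.229) = 0.12. Over all correlated scenarios the range is about 0.04 to 0.4 of 6.

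**Step 5: visibility.** Take the 0.37 case as two binomials with n = 6. The SD of the difference is √(6 × 0.254 × 0.746 + 6 × 0.315 × 0.685) = 1.56 subjects. The 3000 mg count exceeds the 1000 mg count in 47% of trials and is lower in 29%. If both groups had 25.4%, each figure would be 37%.

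**Step 6: placebo and total columns.** If placebo infusions match their cohort's length, pooled placebo averages (22 + 29 + 36)/3 = 29 readings and a probability of (25.4 + 28.5 + 31.5)/3 = 28.5%. That is above 1000 mg, equal to 2000 mg and below 3000 mg. CHF10067 Total has 6 subjects per cohort and the same average, so it is balanced against placebo.

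**Step 7: common schedule only.** Using readings from end of infusion onward (5.5 h case), systolic SD 8 gives 23.2%, 23.8%, 24.1%, and diastolic SD 5 gives 39.1%, 39.5%, 39.2%. The gradient nearly disappears.

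**The case against.** **The premise is partly hidden.** Rate, concentration and durations are redacted or not given. Longer infusions at higher doses are the natural reading of Protocol 6.2.2, but proportionality and 5.5 h at 3000 mg are assumptions, and the last SAP window may include room for slowed or interrupted infusions. This stands: the point is conditional, and with equal durations it vanishes.

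**The effect is small.** It is a fraction of a subject against a sampling SD of about 1.6. The SDs are unsourced, and the SAP analyses means of duplicates, which lowers noise. This stands. A reader might infer that the observed count will rise with dose. The calculations support only a rise in the expected count.

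**Either-direction figures would look larger.** A reader might combine increases and decreases into one any-change probability. SAP 3.3.2 keeps them apart, so no row of the table shows that figure.

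**Placebo is not mismatched to every dose.** A reader might infer that pooling leaves placebo comparable with no dose. On the reading counts above its average equals that of 2000 mg, and the total column is balanced if placebo infusions match their cohorts.

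**Other displays help.** The same table gives each time point separately. Individual plots, full listings and infusion times are also produced, and the enumerated escalation criteria in Protocol 6.2.2.1 rest on adverse events. This is a real mitigation. However, late during-infusion windows would hold mainly longer-infused subjects, so those rows do not readily correct the summary row.

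**Redefining the row has a price.** It would depart from Protocol 12.3.5.6 and drop infusion-period and unscheduled readings from the headline count, although infusion reactions are a named concern. This stands, and the row should be kept.

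**Conclusion.** The point holds in conditional form. If infusion duration increases with dose, the any-time row of Table 14.3.3.2 has an upward gradient in its expected count with no drug effect, and no SAP rule offsets it. The direction was the same in every scenario in which duration rose with dose. Under correlated readings the 1000 to 3000 mg shift is about 0.04 to 0.4 subjects of 6, depending on the assumed SD and longest infusion. The distortion is confined to this row: rows for single time points are not inflated in this way. Unscheduled readings also enter the worst case and could add to the imbalance, but the documents do not allow that to be sized. This is an inexpensive improvement to a key safety display, not a flaw that undermines the safety evaluation.

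**What to change.** In SAP 3.3.3 and Table 14.3.3.2:

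1. Keep the protocol-specified any-post-dose row with all readings, and show the number of readings per subject by treatment.
2. Add a second any-time row limited to time points scheduled for every cohort (end of infusion onward). State that this row is the one for comparing doses with each other and with placebo.
3. Add a separate during-infusion row, so that no infusion-period safety information is lost.

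The cost is programming and extra table rows, with no new data. Keeping the first row preserves what Protocol 12.3.5.6 asks for. The common-schedule row does not capture changes during infusion. Those remain in the other two rows, where reading counts are still unequal and should be read with the counts shown.

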3.4 ELECTROCARDIOGRAMS

3.4.1 *Available data*

The following electrocardiogram (ECG) parameters will be collected:

- Triplicate local 12-lead ECG at Screening: heart rate (HR), PR interval, QRS interval, QT interval, corrected QT interval (Fridericia) (QTcF) and the corresponding interpretation
- Local 12-lead single ECG at other visits: heart rate (HR), PR interval, QRS interval, QT interval, corrected QT interval (Fridericia) (QTcF) and the corresponding interpretation

ECGs will be performed at Screening visit, at pre-dose on Day 1, and Days 2, 7, 28, and 84 days post-dose and in case of early termination visit.

3.4.2 *Derivation rules*

Mean values of the triplicates will be calculated at Screening and rounded as detailed in section 6.3.4. Records belonging to the same triplicate will be identified using variable EGREFID. All records of the triplicate will be used to calculate the mean, even if less or more than the expected three. Throughout the analysis, including the derivation of baseline and abnormalities, the mean values will be used. Individual triplicate values will only be listed.

For QTcF interval (ms), the following abnormality categories are defined:

- Actual values:
 - Males:
 - > 450 ms
 - > 480 ms
 - > 500 ms
 - Females:
 - > 470 ms
 - > 500 ms
- Changes from baseline:
 - Increase from baseline >30 ms
 - Increase from baseline >60 ms

Note: The worst-case, as defined in section 6.2.5, is the highest value and associated change.

3.4.3 *Presentation of results*

Local safety 12-lead ECG parameters (HR, PR, QRS and QTcF) will be summarised by means of descriptive statistics at each analysis time point by treatment. Actual values (with their 95% CI) and changes from baseline (with their 90% CI) will be tabulated.

For QTcF, the number and percentage of subjects with abnormal actual values will be presented at each post-dose time point and at the worst-case post-baseline analysis visit by treatment.

For QTcF, the number and percentage of subjects with abnormal changes from baseline will be presented at each post-dose time point and at the worst-case analysis visit by treatment.

All ECG data will be listed.

Graphs of the mean changes from baseline over time will be prepared for the continuous ECG parameters by treatment. In addition, individual graphs of the changes from baseline over time will be presented by treatment.

3.5 LUNG FUNCTION

3.5.1 *Available data*

The following lung function parameters are collected:

	Statistical Analysis Plan	
CLI-10067AA1-01	Final Analysis	Final 1.0 of 30MAY2024

- Spirometry: Forced Expiratory volume in 1 second (FEV₁), predicted FEV₁, percent predicted FEV₁, forced vital capacity (FVC), predicted FVC, percent predicted FVC and FEV₁/FVC ratio.
Spirometry will be assessed at the following timepoints: screening, 7, 28, 56, and 84 days post-dose and in case of early termination visit.
- Diffusing capacity: D_{LCO} [unadjusted], D_{LCO} % predicted, D_{LCO} corrected for haemoglobin, D_{LCO} corrected for haemoglobin % predicted, carbon monoxide transfer coefficient [KCO], and alveolar volume [VA].
Diffusing capacity will be assessed at the following timepoints: screening, 28, 56, and 84 days post-dose and in case of early termination visit.

3.5.2 *Presentation of results*

Spirometry:

Spirometry parameters will be summarised by means of descriptive statistics (with their 95% CI) at each analysis time point by treatment. Actual values, changes from baseline and relative changes from baseline will be tabulated.

Graphs of the absolute and relative mean changes from baseline over time will be prepared by treatment.

All spirometry parameters will be listed.

Diffusing capacity:

Diffusing capacity parameters will be summarised by means of descriptive statistics (with their 95% CI) at each analysis time point by treatment. Actual values, changes from baseline and relative changes from baseline will be tabulated.

Graphs of the absolute mean changes from baseline over time will be prepared by treatment for D_{LCO} % predicted and D_{LCO} corrected for haemoglobin.

All diffusing capacity parameters will be listed.

3.6 SYSTEMIC MARKERS FOR EVALUATION OF IMMEDIATE HYPERSENSITIVITY REACTIONS

3.6.1 *Available data*

Following systemic markers for evaluation of immediate hypersensitivity reactions will be collected: Cytokine markers (IFN- γ , TNF- α , IL-1 β , IL-2, IL-4, IL-6, IL-8, IL-10, IL-12 (p70), and IL-13), mast cell tryptase, complement markers (C3a, C5a, CH50, and SC5b-9), and CHF10067 IgE.

3.6.2 *Presentation of results*

The statistical analysis will present results in standardised units.

Systemic markers will be summarised by means of descriptive statistics, if data is available for at least 3 subjects, at each timepoint by treatment. Actual values and changes from baseline will be tabulated.

3.7 PHYSICAL EXAMINATIONS

Abnormal physical examination findings will be listed.

4. OTHER VARIABLES

4.1 TG2 IN PLASMA

According to the protocol, the exploratory endpoint of this study is:

- TG2 levels in plasma

4.1.1 *Available data*

TG2 levels in plasma samples be collected pre-dose and on Days 14, 28, 56, and 84.

4.1.2 *Presentation of results*

The statistical analysis will present results in standardised units.

TG2 levels in plasma will be summarised by means of descriptive statistics at each analysis visit by treatment. Actual values (with their 95% CI) and changes from baseline (with their 95% CI) will be tabulated.

Graphs of the mean changes from baseline over time will be prepared by treatment. In addition, individual graphs of the changes from baseline over time will be presented by treatment and ADA positivity/negativity (see definitions in Section 2.2.2).

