1.2 Study Rationale

The development of novel therapies for the treatment of IPF, a rapidly progressive and fatal orphan disease, remains a great challenge despite significant unmet medical need. CHF10067 is being developed to meet this unmet need.

The principal aim of this study is to obtain safety and tolerability data when CHF10067 is administered intravenously as single ascending doses to subjects with IPF. This information, together with the pharmacokinetic (PK) and immunogenicity data, will help establish the doses suitable for future studies in subjects. The effect of CHF10067 on TG2 levels will also be investigated as an exploratory endpoint.

A sequential-group, single ascending dose design has been chosen for safety reasons because CHF10067 is in the early stages of clinical development and no data in the IPF population has been collected so far. In addition, sentinel dosing will be used such that 2 subjects (1 CHF10067 and 1 placebo) in each cohort will be dosed at least 24 hours before the remaining 6 subjects.

The study will be double blind and placebo controlled to avoid bias in the collection and evaluation of data during its conduct. Placebo has been chosen as the comparison treatment to assess whether any observed effects are treatment related or simply reflect the study conditions.

Based upon the preclinical and clinical data and the potential of anti-drug antibody (ADA) response, the planned duration of the treatment period is considered adequate to achieve the study objectives. Subcutaneous doses were tolerated up to a dose of [REDACTED] and IV doses were tolerated up to a dose of [REDACTED]; therefore, IV doses have been chosen for this study. [REDACTED].

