3. STUDY DESIGN

This is a Phase Ib, multi-centre, multi-country, randomised, double-blind, placebo-controlled study to investigate the safety, tolerability, immunogenicity, and PK of single IV doses of CHF10067 in subjects with IPF. The effect of CHF10067 on TG2 levels will also be investigated as an exploratory endpoint.

Overall, 24 subjects will be studied in 3 cohorts (Cohorts A [1000 mg], B [anticipated 2000 mg], and C [anticipated 3000 mg]) consisting of 8 subjects per cohort. In each cohort, 6 subjects will receive CHF10067, and 2 subjects will receive placebo.

The doses will be administered according to an escalation scheme designed to ensure sufficient safety conditions for subjects. In each cohort, subjects will be divided into 2 sub-groups, with each sub-group being dosed at least 24 hours apart. The first sub-group will comprise 2 subjects, with 1 subject receiving CHF10067 and 1 subject receiving placebo. The second sub-group will comprise 6 subjects, with 5 subjects receiving CHF10067 and 1 subject receiving placebo. Continuation to dose the remaining 6 subjects will be evaluated by at least the Medical Monitor and Sponsor Clinical Research Physician based on the safety data provided by the Investigator(s) where the first-sub-group have been dosed. The decision to escalate to the next dose will be made by the Safety Advisory Committee when safety data until Day 14 have been collected for all subjects at the previous dose level. Pharmacokinetic and immunogenicity data will also be included in the safety evaluation for dose escalation (if available) but are not mandatory to escalate to the next dose. Further details regarding dose escalation are provided in [Section 6.2.2.1](#).

[figure not shown]
The screening visit will take place between 3 to 28 days prior to randomisation and subject eligibility will be assessed according to the inclusion/exclusion criteria. The signed informed consent form (ICF) will be obtained prior to any study-related procedures.

On Day 1, subjects will attend the clinical site for an ambulatory visit. Following confirmation of eligibility, subjects will be randomised to either CHF10067 or placebo and will receive a single IV dose of CHF10067 or placebo.

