12.3.6 Other variables

12.3.6.1 TG2 in plasma

At each post-dose timepoint, TG2 levels in plasma will be summarised using descriptive statistics by treatment as absolute value and change from baseline (i.e., the pre-dose assessment on Day 1) using descriptive statistics and 95% CIs.

Time profile plots will be presented by dose level, based on arithmetic means, and by subject, by showing the individual curves grouped by dose level (1 plot for each dose level) and ADA positivity/negativity (using different colours).

The TG2 levels in plasma obtained from healthy subjects will be summarised using descriptive statistics.

Box-plots summarising the pre-dose levels for treated subjects in the study, the healthy subjects' external group, and each post-dose levels for the different doses for treated subjects will be presented.

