1.2 STUDY DESIGN

[figure not shown]
This is a Phase Ib, multi-centre, multi-country, randomised, double-blind, placebo-controlled study to investigate the safety, tolerability, immunogenicity, and PK of single IV doses of CHF10067 in subjects with IPF. The effect of CHF10067 on TG2 levels will also be investigated as an exploratory endpoint.

Overall, 24 subjects will be enrolled in 3 cohorts (Cohorts A [1000 mg], B [anticipated 2000 mg], and C [anticipated 3000 mg]) consisting of 8 subjects per cohort. In each cohort, 6 subjects will receive CHF10067, and 2 subjects will receive placebo.

The doses will be administered according to an escalation scheme designed to ensure sufficient safety conditions for subjects. In each cohort, subjects will be divided into 2 sub-groups, with each sub-group being dosed at least 24 hours apart. The first sub-group will comprise 2 subjects, with 1 subject receiving CHF10067 and 1 subject receiving placebo. The second sub-group will comprise 6 subjects, with 5 subjects receiving CHF10067 and 1 subject receiving placebo. Continuation to dose the remaining 6 subjects will be evaluated by at least the Medical Monitor and Sponsor Clinical Research Physician based on the safety data provided by the Investigator(s) where the first-sub-group have been dosed. The decision to escalate to the next dose will be made by the Safety Advisory Committee when safety data until Day 14 have been collected for all subjects at the previous dose level. Pharmacokinetic and

immunogenicity data will also be included in the safety evaluation for dose escalation (if available) but are not mandatory to escalate to the next dose.

An overview of the study design is shown in the figure below.

The schedule of assessments is in appendix 10.1.

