1.4 RANDOMISATION AND BLINDING

An interactive responsive technology (IRT) system will be used for randomisation and assignment to blind treatment (CHF10067 or placebo).

The Investigator, or designee, at the sites will use the IRT system to screen and randomise subjects and to assign treatment kits according to the randomisation list. Subjects will be randomised in a 3:1 ratio within each cohort to receive either CHF10067 or placebo. Randomisation will require a minimum of 2 subjects within each cohort not receiving antifibrotic treatment (including subjects with previous use of antifibrotic treatment that has been stopped for at least 2 weeks prior to screening). In each cohort, at least 24 hours must elapse between dosing of the first 2 subjects (1 CHF10067; 1 placebo) and the remaining 6 subjects. The IRT system will be used to coordinate the scheduling of Day 1 visits to be sure that this procedure is followed.

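### The plan says the effect of CHF10067 on TG2 will be investigated, but produces no drug-minus-placebo estimate for TG2, only separate summaries for each arm

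*SAP*

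**What the plan says.** On purpose, Protocol 1.2 states: "Placebo has been chosen as the comparison treatment to assess whether any observed effects are treatment related or simply reflect the study conditions". Protocol section 3 adds: "The effect of CHF10067 on TG2 levels will also be investigated as an exploratory endpoint"; SAP 1.2 repeats this. The formal exploratory objective (Protocol 2.3, SAP 1.1) is narrower and asks only for an evaluation of plasma TG2 levels.

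On analysis, SAP 4.1.2 states that "TG2 levels in plasma will be summarised by means of descriptive statistics at each analysis visit by treatment", and then: "Actual values (with their 95% CI) and changes from baseline (with their 95% CI) will be tabulated". Protocol 12.3.6.1 is equivalent: TG2 is reported by treatment "as absolute value and change from baseline (i.e., the pre-dose assessment on Day 1) using descriptive statistics and 95% CIs". Table 14.3.7.1, marked as a key first result, holds actual values and changes from baseline only. Neither document names a TG2 contrast, an interval for one, or a model. The only inferential analysis in the SAP is PK dose proportionality (2.1.3).

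On design: "In each cohort, 6 subjects will receive CHF10067, and 2 subjects will receive placebo". SAP 6.4.2 pools placebo over the three cohorts, and SAP 6.4.3 places it after the active groups. SAP 7.1 drops the protocol's healthy-subject TG2 summary and box-plots, and also its placebo-corrected ECG change.

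**The concern.** An effect of a drug is a contrast with its comparator. A change from pre-dose within one arm mixes any drug effect with whatever else moves TG2 between Day 1 and Days 14 to 84: disease course, regression to the mean, storage or assay drift. Placebo was included to take that out, but no planned estimate uses it for this. A reader of Table 14.3.7.1 is left to set four separate intervals against each other, which is not a valid comparison. TG2 is the antibody's target and the table will be read early, so an informal conclusion about target effect could be drawn from it.

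**Working it through.** **Inputs from the documents.** Three cohorts of 6 active and 2 placebo: 3 × 6 = 18 active, 3 × 2 = 6 pooled placebo, 24 in all. Post-dose TG2 visits are Days 14, 28, 56 and 84, so there are 3 × 4 = 12 dose-by-visit intervals. SAP 6.4.1 bases CIs on the t-distribution; I take this to apply to TG2.

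**Not in the documents.** No TG2 SD, drift, expected effect or power is given, so there is no planned figure to reproduce. Results are in units of the SD of change, and the drift sizes are assumptions shown as a range.

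**Step 1: no drug effect, the same drift d in every arm.** The within-arm interval is mean ± t(0.975, 5) × SD/√6, with half-width 2.571/2.449 = 1.05 SD. The chance p that it excludes zero comes from the noncentral t with 5 df and noncentrality d√6. The chance that a dose interval excludes zero while the placebo interval does not is p(1 − p), since both arms have n = 6 and are independent. The drift cancels in a dose-minus-placebo difference.

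| Drift (SD of change) | Within-arm CI excludes 0 | Expected count of 12 | Dose CI excludes 0, placebo CI does not | Difference CI excludes 0 |
|---|---|---|---|---|
| 0 | 5% | 0.6 | 5% | 5% |
| 0.25 | 8% | 1.0 | 7% | 5% |
| 0.5 | 17% | 2.0 | 14% | 5% |
| 0.75 | 32% | 3.8 | 22% | 5% |
| 1 | 51% | 6.1 | 25% | 5% |

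**Step 2: precision of a difference, before baseline adjustment.** Half-width = t × SD × √(1/n₁ + 1/n₂).

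- One dose versus pooled placebo, variance pooled over four arms (20 df): 2.086 × √(1/6 + 1/6) = 1.20 SD.
- The same from those two arms alone (10 df): 2.228 × 0.577 = 1.29 SD.
- All active versus placebo (22 df): 2.074 × √(1/18 + 1/6) = 0.98 SD.

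ANCOVA on pre-dose TG2 multiplies the SD of change by √(1 − r²)/√(2(1 − r)). This is 0.84, 0.89 or 0.95 at an assumed baseline correlation r of 0.4, 0.6 or 0.8, ignoring the lost degree of freedom and any baseline imbalance.

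**Step 3: drift confined to one cohort.** Only 2 of the 6 placebo subjects come from any one cohort. A 0.75 SD shift in that cohort moves its dose mean by 0.75 but the pooled placebo mean by 0.75 × 2/6 = 0.25, leaving a bias of 0.50 SD. By simulation (variance pooled over four arms), that dose's difference interval then excludes zero about 12% of the time. Comparing within the cohort would remove the bias, but 6 versus 2 (6 df) gives a half-width of 2.447 × √(1/6 + 1/2) = 2.00 SD.

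**The case against.** **The objective is met.** A reader might infer that the exploratory objective cannot be answered. The documents do not support that: the formal objective is about levels, and descriptive statistics by treatment and visit answer it. The mismatch is with the rationale and design text that speaks of an effect. This stands.

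**Placebo is visible.** A reader might also infer that drift would pass unseen. It would not. Pooled placebo is shown next to the doses, Figure 14.3.6.1 plots every treatment, Listing 16.2.13.1 gives individual values and changes, and an unadjusted difference could be computed by hand from the tabulated n, mean and SD of change. This stands, but it is partial protection: by-eye reading still misleads in 14% to 25% of cases at drift of 0.5 to 1 SD.

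**No decision rule exists.** Nothing in either document treats a TG2 interval that excludes zero as proof of a drug effect. The percentages in Step 1 therefore describe how an informal reading would behave; they are not the error rate of a planned test. This stands.

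**The remedy is weak.** With 6 versus 6, a true 1 SD drug effect would give an interval excluding zero only about 38% of the time (20 df), and drift specific to a cohort or assay batch survives in part. Both are true. They are reasons to report an estimate with its interval, not reasons to report none. Whether assay batch matters at all depends on how samples are run, which Protocol 7.2.3 leaves to a separate analytical protocol. If all of a subject's samples share a run, a constant run offset cancels in the change.

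**Conclusion.** The point holds in a limited form. The documents announce an investigation of the drug's effect on TG2 and explain placebo as the means of isolating such effects, then plan no quantity that estimates one. The size depends on assumed drift: with none, within-arm intervals behave as they should (5%); at 0.25 to 1 SD of change common to all arms they exclude zero in 8% to 51% of cases without any drug effect, against 5% for a difference from placebo. That 5% rests on the drift being common to all arms; a 0.75 SD shift in one cohort raises it to about 12%. Severity is low: TG2 is the exploratory endpoint of a 24-subject safety study without a power calculation, and no dose-escalation, primary or secondary conclusion depends on it.

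**What to change.** Add to SAP 4.1.2 and Table 14.3.7.1, labelled exploratory and with no claim based on a test:

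- At each post-dose visit, the difference from pooled placebo with its 95% CI, for each dose and for all active doses together, from an ANCOVA adjusted for pre-dose TG2 (on the log scale, reported as a ratio, if the data are skewed).
- The existing within-arm summaries, kept as they are.
- A note that the intervals will be wide: before baseline adjustment, half-width about 1.2 SD of change per dose with variance pooled over four arms (1.29 SD from two arms alone) and about 0.98 SD for all active doses.
- A note that drift confined to one cohort is only partly removed, because each cohort supplies 2 of the 6 placebo subjects.

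If the team prefers no contrast, one sentence stating that no effect of CHF10067 on TG2 will be inferred would bring the text and the analysis into line. The cost is SAP wording and a few table rows from data already collected; no extra subjects, visits or samples are needed.
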